Acute Oroantral Communication Closure: Resorbable Collagen Membrane vs. Buccal Advancement Flap Outcomes: A Clinical Trial

PCN/0022/KB1/94/20/21

12.02.2021

Study Protocol and Statistical Analysis Plan

Protocol Overview and Rationale

This investigator-initiated, prospective, non-randomized, parallel-group clinical study was designed to compare the clinical effectiveness and early radiographic healing associated with two surgical techniques for closure of acute oroantral communication (OAC) diagnosed within 24 hours after extraction of posterior maxillary teeth. The study was conducted at the Department of Dental Surgery, Faculty of Medical Sciences in Zabrze, Medical University of Silesia. The protocol was approved by the Institutional Review Board (PCN/0022/KB1/94/20/21), and all participants provided written informed consent prior to enrollment.

The study hypothesis was that minimally invasive closure using a resorbable heterogeneous collagen membrane would better preserve soft tissue architecture and reduce postoperative morbidity compared with the conventional Rehrmann buccal advancement flap, while maintaining comparable early bone healing.

Study Population and Enrollment

Consecutive adult patients presenting with acute OAC within 24 hours following extraction of a maxillary posterior tooth were screened for eligibility according to predefined inclusion and exclusion criteria. Twenty-four patients were enrolled; twenty completed the full 90-day follow-up and were included in the final analysis. The mean defect diameter was 3.5 ± 1.0 mm (range 2 to 5 mm), verified clinically and with limited-field CBCT on day 0.

Interventions and Standardization

Participants were assigned to one of two parallel treatment arms based on a predefined clinical protocol and the availability of the membrane technique at the time of treatment. Formal randomization and allocation concealment were not implemented.

All surgical procedures were performed by the same experienced oral surgeon to minimize operator-related variability. Preoperative preparation, socket debridement, smoothing of sharp bony margins, antibiotic prophylaxis, sinus precautions, analgesic recommendations, and follow-up schedules were standardized across both groups.

Experimental arm: closure using submucosal placement of a resorbable heterogeneous collagen membrane (Creos Xenoprotect) stabilized with horizontal mattress sutures following limited mucoperiosteal elevation without vertical releasing incisions.

Control arm: closure using the classical Rehrmann buccal advancement flap involving trapezoidal full-thickness mucoperiosteal flap elevation with vertical releasing incisions and periosteal releasing incision to permit tension-free coronal advancement.

Follow-up Schedule and Data Collection

Clinical assessments were conducted at baseline (day 0) and on postoperative days 1, 7, 14, and 90. The final radiographic assessment using limited-field CBCT was performed at baseline and at 90 days.

Clinical measurements (vestibular depth, keratinized gingiva width, alveolar socket dimensions) were performed using a calibrated WHO periodontal probe by an independent

examiner blinded to the surgical procedure. Examiner calibration was performed prior to study initiation using repeated measurements in a subset of patients.

Radiographic measurements and region-of-interest (ROI) density analyses were conducted by two trained investigators using standardized protocols in Romexis (v6.4) and ImageJ (v1.53k). Discrepancies were resolved by consensus.

Outcome Measures

Primary endpoint:

- Change in vestibular depth from baseline to 90 days.

Secondary endpoints:

- Change in keratinized gingiva width.
- Change in alveolar socket dimensions.
- Postoperative pain intensity measured with the Visual Analogue Scale (VAS) at days 1, 7, and 14.
- Incidence of postoperative complications (swelling, hematoma, epistaxis, wound dehiscence, persistent communication, fistula formation, clinical sinusitis).
- Normalized bone density at the surgical site derived from CBCT.

Radiographic Density Methodology

Because CBCT gray values are not directly equivalent to absolute Hounsfield Units, density measurements were normalized to adjacent cortical bone within the same scan to reduce inter-individual variability and acquisition-related bias. Regions of interest were placed at three standardized vertical levels of the alveolus (crestal, mid-alveolar, and apical). The arithmetic mean of normalized values was used for statistical analysis.

Statistical Analysis Plan

All analyses were performed using STATISTICA version 13.0. Continuous variables are presented as mean \pm standard deviation. Categorical variables are presented as counts and proportions.

Assumption testing:

- Normality assessed with the Shapiro–Wilk test.
- Homogeneity of variance assessed with Levene’s test.

Between-group comparisons:

- Independent-samples t test for normally distributed variables with equal variances.
- Mann–Whitney U test when parametric assumptions were violated.

Multiplicity control:

The primary endpoint retained a two-sided alpha of 0.05. Because multiple secondary endpoints were analyzed, Bonferroni correction was applied for secondary comparisons, and these results were interpreted as supportive.

Handling of missing data:

Only participants who completed the 90-day follow-up were included in the final per-protocol analysis. No imputation of missing values was performed.

Power considerations:

Given the final sample size ($n = 20$), the study was adequately sensitive for detecting large between-group differences in soft tissue outcomes but underpowered for moderate radiographic density effects. Therefore, CBCT density findings were prespecified as exploratory.

Bias Control Measures

- Single experienced surgeon to reduce procedural variability.
- Independent blinded clinical assessor.
- Dual-investigator radiographic analysis with consensus resolution.
- Standardized postoperative management in both arms.
- Objective probe-based measurements at predefined time points.

Safety Monitoring

Participants were monitored at each follow-up visit for adverse events, including infection, dehiscence, hematoma, epistaxis, persistent OAC, fistula formation, and signs of maxillary sinusitis. All complications were recorded prospectively. No serious adverse events related to the interventions were reported.

Ethical Considerations

The study complied with the Declaration of Helsinki and applicable institutional requirements. Participation was voluntary, and patients could withdraw at any time without affecting their treatment. Data confidentiality was maintained throughout the study.

Protocol Limitations

The protocol acknowledges limitations including non-randomized allocation, small sample size, short follow-up duration, and the known constraints of CBCT-derived density measurements. Findings related to bone regeneration are therefore considered hypothesis-generating and require confirmation in adequately powered randomized controlled trials with longer observation periods.

This Statistical Analysis Plan was finalized prior to database lock and outcome analysis.

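### The hypothesis includes comparable bone healing, but the plan gives no margin or interval criterion by which comparability could be judged

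*Combined protocol and SAP*

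**What the plan says.** In the combined protocol and SAP, Protocol Overview and Rationale states a study hypothesis with three parts: better preserved soft tissue, less postoperative morbidity, and both of these "while maintaining comparable early bone healing". It does not define comparable or name the endpoint that carries the bone claim. Outcome Measures lists one radiographic endpoint, among the secondary endpoints: "Normalized bone density at the surgical site derived from CBCT".

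Under Between-group comparisons the Statistical Analysis Plan names two methods: "Independent-samples t test for normally distributed variables with equal variances", and "Mann–Whitney U test when parametric assumptions were violated". Continuous variables are summarised by mean and standard deviation. No margin, equivalence or non-inferiority test, or confidence interval appears anywhere.

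Three further statements bear on the status of the density result:

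- Multiplicity control: "The primary endpoint retained a two-sided alpha of 0.05", while "Bonferroni correction was applied for secondary comparisons, and these results were interpreted as supportive".
- Power considerations: the study is "underpowered for moderate radiographic density effects", and the density findings are labelled exploratory.
- Protocol Limitations: "Findings related to bone regeneration are therefore considered hypothesis-generating", with confirmation needed from adequately powered randomized trials.

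**The concern.** A t test or Mann–Whitney test asks whether the data contradict no difference. Failing to reject does not show that the arms are alike; in a small study it mostly reflects imprecision. A similarity claim needs a statement of how large a difference would still count as comparable, and an interval to set against it. The plan has neither.

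Better soft tissue at no cost to bone is the conclusion a clinical reader would most readily carry away from this trial, and the plan provides no valid route to its bone half. If the density test came out non-significant, nothing in the plan would stop that result from being read as preserved healing, although a moderate deficit in either arm would usually give the same result. If the Bonferroni correction applies to density, it works the wrong way for this purpose: a stricter threshold guards against false claims of difference but makes non-significance more common.

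**Working it through.** The documents state no power figure, effect size, SD or margin for density, so there is no planned figure to reproduce. The check asks how informative a non-significant density result would be.

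**Inputs**

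- Analysed patients: 20 in total (Study Population and Enrollment). The split by arm is not stated. I assume 10:10 and show 6:14 as an unfavourable case, since assignment depended partly on membrane availability.
- Alpha: 0.05 two-sided, the only level the SAP states, and stated for the primary endpoint. The Bonferroni divisor is not stated. Five secondary endpoints are listed, giving 0.05/5 = 0.01. Counting the three VAS days separately gives seven, and 0.05/7 = 0.0071.
- Whether Bonferroni applies to density at all is unclear, because density is both listed as secondary and labelled exploratory. Both levels are therefore shown.
- Effects in SD units: 0.5 (moderate) and 0.8 (large). These are assumptions.

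**Chance of a non-significant result (t test)**

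Power = P(T > t(1−α/2, 18)), where T is noncentral t with 18 degrees of freedom and noncentrality d / √(1/n1 + 1/n2). The opposite tail adds at most 0.002 and is ignored.

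For 10:10 and d = 0.5, √(1/10 + 1/10) = 0.447 and the noncentrality is 0.5/0.447 = 1.118. The critical value is 2.101 at alpha 0.05 and 2.878 at 0.01. Power is 0.184 and 0.060, so the chance of non-significance is 1 − 0.184 = 82% and 1 − 0.060 = 94%.

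For 6:14, √(1/6 + 1/14) = 0.488 and the noncentrality is 0.5/0.488 = 1.025. Power is 0.161 and 0.050.

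| True difference | Split | Non-significant at 0.05 | at 0.01 | at 0.0071 |
|---|---|---|---|---|
| 0.5 SD | 10:10 | 82% | 94% | 95% |
| 0.5 SD | 6:14 | 84% | 95% | 96% |
| 0.8 SD | 10:10 | 60% | 83% | 86% |
| 0.8 SD | 6:14 | 66% | 86% | 89% |
| 1.0 SD | 10:10 | 44% | 71% | 75% |

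The difference detectable with 80% power at 10:10 is 1.33 SD at alpha 0.05 and 1.69 SD at 0.01. This agrees with the SAP's own admission about moderate density effects.

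**Precision**

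Half-width of the 95% interval = t(0.975, 18) × √(1/n1 + 1/n2), in SD units.

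- 10:10: 2.101 × 0.447 = 0.94 SD.
- 6:14: 2.101 × 0.488 = 1.03 SD.

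An observed difference of exactly zero would still be compatible with a true difference of nearly one SD in either direction.

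**Could 20 patients show comparability if a margin were set?**

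The documents give no margin, so a range is shown. The table assumes truly identical arms. Equivalence is judged by two one-sided tests at 0.05 each (the 90% interval lying wholly inside the margin). Power at 10:10 was simulated. The sample size for 80% power is n per arm = 2 × ((1.645 + 1.282)/margin)², with the margin in SD units, rounded up.

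| Margin | Power at 10:10 | n per arm for 80% power |
|---|---|---|
| 0.5 SD | 0.1% | 69 |
| 0.8 SD | 12% | 27 |
| 1.0 SD | 39% | 18 |

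Power reaches 89% only at a margin of 1.5 SD, nearly twice the effect taken here as large.

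**The case against.** The strongest reply is that the documents already warn against over-reading density. The SAP concedes that the study is underpowered for moderate effects and makes density exploratory, and Protocol Limitations defers bone conclusions to larger randomized trials. The full alpha is reserved for vestibular depth. The primary endpoint and its analysis are untouched.

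Most of this stands. A reader might infer that the plan will count a non-significant density result as proof of comparable healing. No section says so, and no decision rule of that kind can be attributed to the authors. Nor do the documents declare the bone claim confirmatory: it is part of a study hypothesis whose radiographic endpoint is openly exploratory. It would also be too broad to say that any deficit would normally be missed. At 10:10 and alpha 0.05, a difference of 1.0 SD is missed 44% of the time and one of 1.33 SD 20% of the time.

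The labels still do not supply what is missing. They lower the weight of the density result without saying what result would count as comparable, and they do not rule out reading non-significance that way. The comparability claim in the hypothesis carries no qualification of its own.

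**Conclusion.** The point holds in this form: the comparability part of the hypothesis has no criterion, the planned tests cannot supply one, and a non-significant density result with 20 patients would say little about similarity. At 10:10, a 0.5 SD difference would be missed about 82% of the time at alpha 0.05, and the 95% interval would extend about 0.94 SD either side of the estimate.

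The split, the Bonferroni divisor, its application to density, and the effects and margins in SD units are all assumptions. The direction of the conclusion does not change over the ranges shown. The figures are for the t test; the Mann–Whitney branch was not computed. Taking normalized density as the carrier of the bone claim is a reading of the documents, since it is the only radiographic endpoint listed.

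This should be fixed, but it is not critical. It concerns what may be concluded about an exploratory endpoint and leaves the primary analysis intact.

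**What to change.** - Report the between-arm difference in normalized density with a 95% confidence interval, as the exploratory result.
- Do not use the Bonferroni-corrected p-value to judge similarity.
- State in the SAP, as a dated addition, and in the conclusions that p > 0.05 for density will not be described as comparable, equivalent or maintained bone healing.
- Keep the hypothesis on record as written, and state beside it that 20 patients cannot establish its comparability part.

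Enrolment and 90-day follow-up are reported as complete. Deleting part of the hypothesis now would be retrospective rewriting, and a margin chosen now would come after data collection. Neither is recommended, and the equivalence figures show that a margin of 1.0 SD or less would very probably not be met anyway.

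The cost is a few sentences and one interval, with no new data. The sponsor gives up a conclusion of comparable bone healing, which a trial of this size could not support at any margin up to 1.0 SD except by luck.

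### Treatment was assigned without randomization by an undescribed rule, but only unadjusted tests are planned, so the primary comparison is open to confounding of unknown size

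*Combined protocol and SAP*

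**What the plan says.** The combined protocol and SAP describes a "prospective, non-randomized, parallel-group clinical study" (Protocol Overview and Rationale). Under Interventions and Standardization, patients went to an arm "based on a predefined clinical protocol and the availability of the membrane technique at the time of treatment", and "Formal randomization and allocation concealment were not implemented". The content of that clinical protocol is not given.

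The primary endpoint (Outcome Measures) is "Change in vestibular depth from baseline to 90 days". It is tested at a two-sided alpha of 0.05 (Multiplicity control). Between-group comparisons names two methods: "Independent-samples t test for normally distributed variables with equal variances" and "Mann–Whitney U test when parametric assumptions were violated". The plan has no covariate, matching, stratification, period term or baseline comparison by arm.

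Bias Control Measures lists five items: one surgeon, a blinded clinical assessor, dual radiographic reading, uniform aftercare and probe-based measurement. Protocol Limitations names the lack of randomization, but it applies the hypothesis-generating label to the bone findings and not to the soft-tissue primary endpoint.

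Baseline information exists. Vestibular depth is needed at day 0 to form the change. Defect diameter, given as 3.5 ± 1.0 mm (range 2 to 5 mm) for both arms together, was "verified clinically and with limited-field CBCT on day 0" (Study Population and Enrollment).

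**The concern.** Where chance does not decide the arm, the two groups may differ in things that affect healing. Availability of the membrane links arm to calendar time. The undescribed clinical protocol may link arm to defect size or anatomy, and the reader cannot tell. A two-sample test attributes all of the difference between the groups to the operation. The five bias-control measures deal with how surgery was done and how outcomes were measured. They leave the selection of patients into arms untouched.

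What is at stake is the only endpoint carrying a full 5% alpha. If a prognostic factor differs systematically by arm, the test no longer holds that level and the estimate is shifted, in a direction that cannot be known from the documents.

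**Working it through.** The plan states no numerical power or effect size, so there is no figure of its own to reproduce. The question is how much a given bias would matter.

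**Inputs from the documents:** 20 patients analysed of 24 enrolled; two-sided alpha 0.05; primary endpoint a change score; pooled defect SD 1.0 mm.

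**Assumptions:** 10 per arm (arm sizes are not given); no true effect; every imbalance and correlation below.

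**Step 1. False-positive rate for a given bias.** Let b be the bias in within-arm SDs of the outcome. The t statistic has 18 degrees of freedom and noncentrality b / √(1/10 + 1/10) = b / 0.447. The probability of rejecting in either direction is:

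| Bias b | Noncentrality | False-positive rate |
|---|---|---|
| 0 | 0 | 5.0% |
| 0.1 | 0.22 | 5.5% |
| 0.3 | 0.67 | 9.7% |
| 0.4 | 0.89 | 13.5% |
| 0.5 | 1.12 | 18.5% |

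The assumed split matters little: at b = 0.5 the rate is 18.0% for 12:8 and 16.3% for 14:6.

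**Step 2. What produces such a bias through defect size.** b = imbalance (in within-arm SDs) × correlation of diameter with outcome.
- Imbalance 1.0, correlation 0.3 / 0.4 / 0.5: b = 0.30 / 0.40 / 0.50, the rates above.
- Imbalance 0.5, correlation 0.3 / 0.5: b = 0.15 / 0.25, rates 6.2% / 8.3%.

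The stated 1.0 mm is a pooled SD. If it describes the 20 analysed patients, a 1.0 mm gap between arms of 10 leaves a within-arm variance of (19 − 5)/18 = 0.78, an SD of 0.88 mm. The gap is then somewhat more than 1 within-arm SD.

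**Step 3. Baseline depth.** The change score already subtracts baseline. With equal SDs at both times and day-90 depth regressing on baseline with slope ρ, an imbalance Δ leaves (ρ − 1)Δ in the difference. The SD of change is √(2(1 − ρ)), so the standardized size is Δ√((1 − ρ)/2).

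| ρ | Δ = 0.5 SD | Δ = 1.0 SD |
|---|---|---|
| 0.5 | 0.25, rate 8.3% | 0.50, rate 18.5% |
| 0.7 | 0.19, rate 7.0% | 0.39, rate 13.0% |
| 0.9 | 0.11, rate 5.6% | 0.22, rate 7.6% |

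**Step 4. What adjustment does.** In simulations with one measured confounder (4,000 replicates per setting, imbalance 0 to 1.0 SD, correlation 0.3 to 0.7), the adjusted test rejected in 4.3% to 5.5% of null trials.

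**Step 5. What adjustment costs.** With balanced baselines, ANCOVA variance relative to the change score is (1 − ρ²)/(2(1 − ρ)) = (1 + ρ)/2. An imbalance of d within-arm SDs multiplies this by 1 + 5d²/18.
- d = 0.5: 0.75 × 1.069 = 0.80 at ρ = 0.5; 0.85 × 1.069 = 0.91 at ρ = 0.7.
- d = 1: 0.75 × 1.278 = 0.96 at ρ = 0.5; 0.85 × 1.278 = 1.09 at ρ = 0.7.
- Defect diameter, d = 1, correlation 0.4, against no adjustment: (1 − 0.16) × 1.278 = 1.07.

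So where the bias is largest, the precision gain shrinks or reverses. The reason to adjust is bias.

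**The case against.** Five arguments count on the other side.

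- **No imbalance is shown.** The assignment rule is undescribed and no baseline values are given by arm. If availability alone decided the arm, defect size and depth need not differ. This stands: a reader might infer that clinical features drove allocation, or that the arms did differ, and the documents establish neither. It is also why the rule and a by-arm table are needed.
- **The change score already protects against baseline-depth differences.** In part. A reader might infer that such differences pass whole into the effect, but only the 1 − ρ share remains. Defect size and period get no such protection.
- **ANCOVA is not automatically right without randomization.** If the arms come from populations with stable differences in depth, the change score can be unbiased and ANCOVA biased, more so with probe measurement error. This stands, and it argues for showing both.
- **Replacing the primary test now would be post hoc,** because the SAP is declared final before database lock. This stands, so the adjusted analysis belongs beside the planned one.
- **The limitation is acknowledged.** It is, but with no analytic response, and the cautious label covers only the bone findings.

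Two further limits apply. Not every endpoint is covered by the named tests, since none is given for the categorical complications. And density, listed as "Normalized bone density at the surgical site derived from CBCT" with no baseline term, is already exploratory, so it does not aggravate the problem.

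**Conclusion.** The point holds as a gap in the analysis plan. Assignment was non-random by an undescribed rule, the named tests are unadjusted, and no bias-control measure addresses confounding. Imbalance in defect size or calendar period, or the 1 − ρ share of an imbalance in baseline depth, can bias the primary comparison.

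The size is conditional. The 9.7% to 18.5% range belongs to an assumed bias of 0.3 to 0.5 SD with an assumed 10 per arm; at 0.1 SD the rate is 5.5%. A reader might infer that the trial's actual error rate is inflated by this much, or that adjustment brings precision for free. The documents support neither: the first needs by-arm data they do not give, and the second fails under the very imbalance that makes adjustment necessary.

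**What to change.** 1. State the assignment rule, and report baseline vestibular depth, day-0 defect diameter and treatment dates by arm.
2. Add a linear model of day-90 vestibular depth on arm, baseline depth and day-0 defect diameter. Report the adjusted difference with its 95% CI beside the planned unadjusted change comparison. Label it post hoc if outcomes have been seen.
3. Base the primary conclusion on whether the two analyses agree, and word it as a non-randomized association.
4. If availability split the arms in time, say that period cannot be separated from treatment; the model above has no time term, and no model could separate them then. Restrict the controls to those treated while the membrane was available only if the dates allow it. The documents mention no availability log, and among 20 patients that subset may be tiny or empty.
5. As a minor addition, adjust normalized density for its day-0 scan value.

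Cost: SAP wording and a short additional analysis. Baseline depth and defect diameter are already collected; treatment dates must be retrievable. Residual degrees of freedom fall by 2, from 18 to 16, and the interval may widen if the arms are imbalanced. Confounding by unmeasured factors remains.

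### The socket-dimension endpoint is assigned to a periodontal probe, which cannot follow the bony socket once the site has closed; the CBCT scans at both time points can

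*Combined protocol and SAP*

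**What the plan says.** Under Follow-up Schedule and Data Collection, one blinded examiner and one instrument cover three clinical measures: "Clinical measurements (vestibular depth, keratinized gingiva width, alveolar socket dimensions) were performed using a calibrated WHO periodontal probe". No other instrument is named for socket dimensions.

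Under Outcome Measures, the secondary endpoint reads in full: "Change in alveolar socket dimensions". It carries no time point, whereas the primary endpoint does: "Change in vestibular depth from baseline to 90 days". The visit schedule offers several candidate days: "Clinical assessments were conducted at baseline (day 0) and on postoperative days 1, 7, 14, and 90".

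Patients enter within a day of extraction (Protocol Overview and Rationale), and both procedures are described as closures. The control arm raises a full-thickness flap with a "periosteal releasing incision to permit tension-free coronal advancement". In the experimental arm the membrane lies beneath the mucosa and is "stabilized with horizontal mattress sutures following limited mucoperiosteal elevation without vertical releasing incisions".

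Imaging exists at both ends of follow-up: "The final radiographic assessment using limited-field CBCT was performed at baseline and at 90 days". Two investigators make radiographic measurements as well as density readings, but the plan does not link those measurements to the socket-dimension endpoint.

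**The concern.** The name of the endpoint suggests a measurement of the alveolus, but the stated method is a probe. If the probe enters an open socket at baseline and later rests on healed mucosa, the difference between the readings mixes bone change with the thickness and shape of the covering tissue.

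The study hypothesis includes comparable early bone healing. CBCT density is declared exploratory and underpowered, so socket dimension is the one other listed endpoint that a reader could take as evidence on alveolar healing. For a claim of comparability, a measurement that hides a real difference does as much harm as one that creates a false difference. Blinding the examiner does not help, because the problem lies in what the probe can reach. Protocol Limitations mentions the constraints of CBCT density but not this one, and Bias Control Measures counts the probe readings as a safeguard.

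**Working it through.** The plan gives no effect size, SD or power figure for socket dimensions, so there is no stated figure to reproduce. The check is mainly one of reasoning, followed by an illustration.

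**Step 1. What the probe can reach.**

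| Time | State of the site | What a probe reaches | Basis |
|---|---|---|---|
| Day 0, before closure | Open socket | The socket itself | Entry criterion; timing of the probing is not stated |
| After successful closure, flap arm | Covered | Mucosal surface | Inferred from the description of closure |
| After successful closure, membrane arm | Covered | Mucosal surface | Inferred from the description of closure |
| CBCT, day 0 and day 90 | Any | Not applicable; images bone at both times | Follow-up schedule |

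Mucosal cover at follow-up is not described in so many words. It is what closure means here, since persistent communication, dehiscence and fistula are all listed as complications.

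**Step 2. What the recorded change contains.** Let B0 be the bony dimension probed in the open socket, Bt the bony dimension at follow-up, and m the difference between the surface reading and Bt. Then:

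- recorded change = (Bt + m) − B0 = (Bt − B0) + m
- between-arm difference in recorded change = true difference + (mean m in flap arm − mean m in membrane arm)

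Two results follow. The within-patient change is off by m whatever happens between the arms. The between-arm comparison is biased only if mean m differs by arm.

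**Step 3. Illustration of the second result.** All inputs in this step are assumptions except the total of 20 analysed and the two-sided 0.05. Arm sizes are not stated, so 10 and 10 is assumed. SDs of the change of 0.5, 1.0 and 1.5 mm are assumed, as are arm-related offsets b of 0.25, 0.5 and 1.0 mm with no true difference. The Bonferroni divisor is not stated. Five secondary endpoints are listed, so 0.05/5 = 0.01 is used as one possibility.

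The probability of a significant result in the direction of the offset comes from the noncentral t distribution with 10 + 10 − 2 = 18 degrees of freedom and noncentrality (b/SD)/√(1/10 + 1/10). For b = 1.0 and SD = 1.0, that is 1/0.447 = 2.24.

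| SD (mm) | b (mm) | alpha 0.05 | alpha 0.01 |
|---|---|---|---|
| 0.5 | 0.25 | 0.18 | 0.06 |
| 0.5 | 0.5 | 0.56 | 0.29 |
| 0.5 | 1.0 | 0.99 | 0.93 |
| 1.0 | 0.25 | 0.08 | 0.02 |
| 1.0 | 0.5 | 0.18 | 0.06 |
| 1.0 | 1.0 | 0.56 | 0.29 |
| 1.5 | 0.25 | 0.05 | 0.01 |
| 1.5 | 0.5 | 0.11 | 0.03 |
| 1.5 | 1.0 | 0.29 | 0.11 |

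With no offset, the corresponding values are 0.025 and 0.005 per tail. The table shows how sensitive the test would be to such an offset. It is not evidence that one exists.

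**The case against.** The strongest reply is that the dimension is undefined, so the endpoint cannot be called invalid. An external ridge width or height taken over soft tissue at both visits would be comparable over time. That stands, and it is why the point is put conditionally. It does not rescue the endpoint as named, because an external soft-tissue measure is not a socket dimension. On either reading the plan needs a definition or a new label.

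A reader might go further and infer that the comparison is biased by technique, for instance because the flap covers the socket at surgery while the membrane site stays open. The documents do not support this. Both procedures are described as closures, the membrane is placed beneath the mucosa and sutured, and nothing says its site is left open. If probing precedes closure, both arms start open and both are meant to end closed. Bias between arms then needs a difference in tissue thickness or contour. That is plausible given the different surgery, but no such difference is reported.

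A reader might also scale an assumed soft-tissue thickness against the 3.5 mm mean defect diameter. That figure describes the oroantral communication, not the socket, and gives no measure of error in this endpoint.

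Two further replies stand. The endpoint is secondary, Bonferroni-corrected and treated as supportive, and no section expressly uses the probe reading as evidence of bone healing. Follow-up is also reported as complete and the SAP as final, so a new definition now is a change that must be declared.

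**Conclusion.** The concern holds in a limited form. As specified, the probe-based change cannot be read as a change in the bony socket, because after successful closure in either arm the probe reaches only the surface and nothing in the plan makes the two readings comparable. This rests on two inferences: that the baseline reading enters an open socket, and that closed sites are covered by mucosa at follow-up.

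Bias in the between-arm comparison is possible but not shown. Its size is unknown. Under the stated assumptions, the chance of a spurious significant result in the direction of the offset runs from little above nominal (0.05 against 0.025 per tail, for 0.25 mm with SD 1.5 mm) to near certainty (0.99, for 1.0 mm with SD 0.5 mm) at alpha 0.05. An offset equal in both arms would leave the comparison intact and distort only the within-patient change.

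One supportive secondary endpoint is affected. The primary endpoint, vestibular depth, is not.

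**What to change.** 1. State what was probed: the dimension, the landmarks, the follow-up day, and whether the day-0 reading was taken before or after closure.
2. Measure alveolar height and width in matched planes on the day-0 and day-90 CBCT scans, where the field of view allows. Use the two existing readers, masked to arm where feasible. If linear measurements already exist among the radiographic measurements, say so and use them.
3. Report the CBCT result as the socket-dimension finding, labelled as a later or supplementary definition because follow-up is already complete.
4. Keep and report the probe value, relabelled as soft-tissue ridge contour, and do not cite it as evidence of socket or bone healing.
5. Add the limits of probing a closed site to Protocol Limitations.

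No new visit, scan or reader is needed. The cost is some added reading time and a declared change of endpoint definition. The documents do not show whether matched planes can be obtained from every limited-field scan, so any patients who cannot be measured should be counted and reported by arm.
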